8. TREATMENT OF PATIENTS

8.1 Investigational Medicinal Product

This is a blinded randomized clinical study with two treatment groups consisting of 0.50 mg/kg Reltecimod and placebo. Patients will be randomized in a 1:1 ratio. Each patient will be administered a single intravenous infusion of Reltecimod based on actual body weight to be infused over 10 minutes at a rate dependent on the dosing volume. Volume of administration will depend on the patients' actual body weight.

The study drug should be administered within 6 hours of the laboratory confirmed diagnosis of Stage 2 or 3 AKI as established at the study site, only after the decision is made by the attending surgeon at the study site for a surgical or interventional radiology procedure for the abdominal infection or after confirmed diagnosis of abdominal infection has been established by a surgical or interventional radiology procedure; or after surgical confirmation of NSTI as described in the inclusion criteria (Section 6.1).

Reltecimod will be supplied in glass vials as a lyophilized powder to be reconstituted with sterile WFI. Drug will be reconstituted on the day of its administration, in close proximity to infusion time, and several vials will be pooled together to compose the requested dose. Final volume for infusion will be based on the patient's actual body weight plus adequate priming volume of the IV line.

Placebo will be pyrogen-free, preservative-free sterile 0.9% saline, USP administered as a single infusion at a volume calculated and based on the patient's actual body weight, 0.50 mL/kg (a volume equivalent with Reltecimod dosing schema), plus adequate priming volume of the IV line.

8.1.1 Presentation and Formulation

Reltecimod is the sodium salt of a 10 amino acid synthetic peptide. Reltecimod has homology to amino acid residues 8-15 of the T-lymphocyte molecule CD28 and has D-Ala residues abutted to N- and C-termini to render them more protease resistant. The final formulated drug product is a lyophilized powder, formulated to contain 1 mg/mL of the Reltecimod peptide, 30 mg/mL mannitol, and 3.6 mg/mL sodium chloride after reconstitution with sterile WFI.

The drug product is filled into clear, 20 mL Type I glass vials with a 20 mm neck and is then lyophilized. Flurotec-coated rubber lyophilization stoppers are used and 20 mm white aluminum overseals.

Each vial of drug contains nominal amounts of the drug substance and excipients as follows: 10.5 mg of Reltecimod, 315 mg of mannitol, and 37.8 mg of NaCl. Prior to use,

each vial of drug product (10.5 mg Reltecimod) is reconstituted in 10.5 mL of water for injection to generate a peptide concentration of 1 mg/mL.

The reconstituted drug product is administered directly and is not diluted prior to administration. To prepare the drug quantity needed for infusion, the contents of several vials are pooled together by the study pharmacist (or unblinded study-nurse/physician if performing study drug preparation at individual institution), under sterile conditions. The number of vials would depend on the patient's actual body weight, in order to achieve a dose of 0.50 mg/kg. The Reltecimod drug product will be administered at a dose of 0.50 mg/kg via a syringe pump (may be manually pushed if approved by the medical monitor) in a separate catheter as a single intravenous infusion given over 10 minutes.

The manufacturer of the clinical batches of the drug substance is PolyPeptide Laboratories, Inc., Torrance CA. The manufacturer of the drug product is Emergent BioSolutions Inc, Baltimore, MD.

8.1.2 Storage

IMP will be stored in a limited access area, under appropriate environmental conditions. Reltecimod should be stored at $-20^{\circ}\text{C} \pm 5^{\circ}\text{C}$ in a secure, temperature-monitored freezer located in Investigational Drug Service or main pharmacy. Reconstituted investigational agents may be stored at room temperature for up to 6 hours. Study drug infusion should be performed as soon as possible but within the 6-hour window previously described. If reconstituted drug is not administered, it should be discarded.

8.1.3 Administration

Formulation and/or preparation of Reltecimod or placebo will be performed by the clinical site pharmacist (or unblinded study-nurse/physician if performing study drug preparation at individual institution). This process will be performed so that the clinical staff and Investigators will be blinded to each patient's treatment assignment and only the pharmacist (or unblinded study-nurse/physician if performing study drug preparation at individual institution) will be unblinded. Administration will be by intravenous infusion using a syringe pump (may be manually pushed if approved by the medical monitor) over a 10-minute period. RRT may be started prior to study drug administration as long as the patient is off RRT during study drug administration and up to at least one hour post study drug administration.

8.1.4 Accountability and Destruction of Surplus Investigational Product

Authorization of the site to receive supplies of IMP will be given by Atox Bio/designee upon receipt of relevant essential documentation (for details refer to the Study Procedure Manual). A designated individual at each site will maintain a log of IMP dispensed for each patient. In addition, the Investigator or designated individual at each site will maintain an IMP Accountability Log. This will include the description and quantity of IMP received at the study site, as well as a record of when and to whom it was dispensed.

All used and unused supplies will be retained at the investigational site until the study monitor gives instructions for their disposal or return. The IMP supplied for this study is

investigational and under no circumstances may be used for purposes other than those described in this protocol.

The Investigator agrees not to supply the IMP to any person other than the patients participating in the study. IMP may not be relabeled or reassigned for use by other patients except under special circumstances previously approved by Atox Bio.

The Investigator will retain and store all original vials until these vials are inventoried by the unblinded study site monitor. Unless otherwise instructed by the Atox Bio medical monitor, the Investigator agrees to destroy (per the site's drug destruction policy) all original vials at the end of the study, whether empty or containing IMP, to Atox Bio or designee. The Investigator agrees neither to dispense the IMP from, nor store it at any site other than the study sites agreed upon.

A separate unblinded study monitor will ensure proper disposition of original vials whether empty or full of IMP. Appropriate IMP disposition documentation will be maintained as part of the source documentation.

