Investigational Product: Type, Dose and Mode of Administration	
Reltecimod is the sodium acetate salt of a 10-amino acids synthetic peptide that is homologous to specific amino acid residues of the T-lymphocyte receptor CD28.
 
Reltecimod is packaged in glass vials as a lyophilized powder to be reconstituted with 10.5 mL of sterile water for injection (WFI) to a concentration of 1 mg/mL. Each vial contains 10.5 mg of Reltecimod with an excipient to protect the peptide during the lyophilization process. Sterile WFI should be obtained by the site pharmacy.
 
The dose of Reltecimod will be 0.50 mg/kg, administered as a one-time dose, with drug administration initiated within the 6-hour time-window from the diagnosis of SA-AKI, only after the decision is made by the attending surgeon at the study site for a surgical or interventional radiology procedure for the abdominal infection or after confirmed diagnosis of abdominal infection has been established by a surgical or interventional radiology procedure; or after surgical confirmation of NSTI as described in the inclusion criteria.
 
Drug will be reconstituted on the day of its administration, in close proximity to infusion time, and several vials will be pooled together to compose the requested dose. Drug will be administered as an intravenous infusion, separate from other medications, over 10 minutes using a syringe pump (may be manually pushed if approved by the medical monitor). Volume of administration will be dependent on the patients' actual weight plus adequate priming volume of the IV line.
 
Placebo for Reltecimod is pyrogen-free and preservative-free sterile 0.9% sodium chloride solution, USP. This should be obtained by the local pharmacy. The volume of blinded placebo should be calculated similarly as for the active group according to the patient's actual body weight (0.50 mL/kg), plus adequate priming volume of the IV line.

---	--

Flow Chart

Study design from clinical presentation to study drug administration for patients with abdominal infection or necrotizing soft tissue infection and confirmed Stage 2 or 3 AKI.

Study Visits		
	Visit	Study Day
	1	Screening
	2	Day 1 Begins with study drug administration and ends with the same calendar day
	3	Day 2
	4	Day 3
	5	Day 7 (± 1 day)
	6	Day 10 (± 1 day) Perform only if patient is still hospitalized
	7	Day 14 (± 1 day)
	8	Day 21 (± 1 day)
	9	Day 29 (+3 days)
	10	3 to 21 Days after Visit 9

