4.3.1 Investigational Medicinal Product (IMP)

Reltecimod drug product is an injection, powder, lyophilized, for solution dosage form. It is formulated to contain 1 mg/mL of the Reltecimod peptide, 30 mg/mL mannitol, and 3.6 mg/mL sodium chloride after reconstitution with sterile WFI. The drug product to be used in clinical trials will be supplied in 20 mL vials. Each vial contains nominal amounts of the drug substance and excipients as follows: 10.5 mg of Reltecimod, 315 mg of mannitol, and 37.8 mg of NaCl.

Prior to use, each vial of drug product (containing 10.5 mg Reltecimod) is reconstituted in 10.5 mL of sterile WFI to generate a peptide concentration of 1 mg/mL. 10 mL of reconstituted solution (containing 10 mg Reltecimod) will be withdrawn from each vial and pooled together with 10 mL from additional reconstituted vials, to constitute the final amount (volume) of drug needed for each patient (based on individual patient’s actual body weight).

The reconstituted drug product is administered directly and is not diluted prior to administration. The Reltecimod drug product will be administered as a single intravenous infusion at a dose of 0.50 mg/kg based on the patient’s actual body weight. The drug product is infused over 10 minutes at a rate dependent on the dosing volume.

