9.2.11.6 Renal Replacement Therapy Guidelines

Renal replacement therapy guidelines are provided only to guide the clinicians. Initiation and stopping of renal replacement therapy can occur based on the clinicians/institution's protocols/judgement. Continuous and intermittent-non-continuous modalities such as intermittent hemodialysis (IHD) are allowed after administration of study drug. RRT may be started prior to study drug administration as long as the patient is off the treatment from time of study drug administration and up to at least one hour post study drug administration.

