13.4 Data Collection

The Investigators (and appropriately authorized staff) will be given access to an online web-based EDC system which is compliant with 21 CFR Part 11. This system is specifically designed for the collection of the clinical data in electronic format. Access and right to the EDC system will be carefully controlled and configured according to each individual's role throughout the study. In general, only the Investigator and authorized staff will be able to enter data and make corrections in the eCRF/EDC system.

The EDC system/eCRF should be completed for each patient included in the study and should reflect the latest observations on the patients participating in the study. Therefore, the EDC system/eCRFs are to be completed as soon as possible (within 5 working days) after the patient's visit or assessment. The Investigator must verify that all data entries in the EDC system/eCRFs are accurate and correct. If some assessments cannot be done, or if certain information is unavailable, not applicable or unknown, the Investigator should indicate this in the EDC system/eCRFs.

Computerized data-check programs and manual checks will identify any clinical data discrepancies for resolution. Corresponding queries will be loaded into the system and the site will be informed about new issues to be resolved online. All discrepancies will be solved online directly by the Investigator or by authorized staff. Off-line edit checks will be done to examine relationships over time and across panels to facilitate quality data.

After completion, the Investigator will be required to electronically sign off the clinical data.

Data about all study drug dispensed to the patient will be tracked on the EDC system/eCRFs.

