13.5 Access to Source Data

During the study, a monitor will make site visits to review protocol compliance, compare EDC system/eCRFs entries and individual patient's medical records, assess drug accountability, and ensure that the study is being conducted according to pertinent regulatory requirements. EDC system/eCRFs entries will be verified with source documentation. The review of medical records will be performed in a manner to ensure that patient confidentiality is maintained, and the study blind is respected.

Checking of the EDC system/eCRFs entries for completeness and clarity, and cross-checking with source documents, will be required to monitor the progress of the study. Moreover, Regulatory Authorities of certain countries, IRBs, IECs, and/or the Sponsor's Clinical Quality Assurance Group may wish to carry out such source data checks and/or on-site audit inspections. Direct access to source data will be required for these inspections and audits; they will be carried out giving due consideration to data protection and medical confidentiality. The Investigator assures the Sponsor of the necessary support at all times.

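### Protocol 8.1.4 gives custody of the trial vials, and optionally the accountability log, to the Investigator, who must stay blinded, although only active doses use trial vials

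*Protocol*

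**What the plan says.** **Where the product comes from.** Active doses are pooled from trial-supplied vials. Protocol 4.3.1 says that "10 mL of reconstituted solution (containing 10 mg Reltecimod) will be withdrawn from each vial", and 8.1.1 makes the number of vials depend on body weight at 0.50 mg/kg. Placebo is 0.9% saline, of which the Synopsis says "This should be obtained by the local pharmacy". Its volume is matched at 0.50 mL/kg (4.3.2, 8.1).

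**Who may know the allocation.** Section 8.1.3 keeps clinical staff and Investigators blinded and says "only the pharmacist (or unblinded study-nurse/physician if performing study drug preparation at individual institution) will be unblinded". Sections 4.3 and 7.2 agree, and 7.2 adds the sponsor and all other study personnel to those who stay blinded.

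**Who holds the vials and records (8.1.4).**
- Vials: "The Investigator will retain and store all original vials until these vials are inventoried by the unblinded study site monitor". The Investigator also agrees to destroy all original vials, empty or not, at the end of the study. Neither sentence names a delegate.
- Accountability log: "the Investigator or designated individual at each site will maintain an IMP Accountability Log". It covers product received and when and to whom it was dispensed.
- Per-patient dispensing log: kept by a designated individual whose blinding status is not stated.
- Monitoring: the study monitor, with no blinding label, instructs on disposal. The same section also provides a separate unblinded monitor for vial disposition.
- Disposition documents form part of the source documentation.

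**Elsewhere.** Section 13.5 has a monitor compare EDC entries with medical records and also "assess drug accountability, and ensure that the study is being conducted according to pertinent regulatory requirements". Section 13.4 says: "Data about all study drug dispensed to the patient will be tracked on the EDC system/eCRFs".

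**The concern.** Trial vials exist for one arm only, so a record of their use by patient is in effect an allocation list. Section 8.1.4 places the vials with a person whom 8.1.3 requires to be blinded, and lets that person keep the log that links them to patients.

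The blind matters here because freedom from dialysis at Day 28 is a component of the primary endpoint, and dialysis is left to local judgement. Section 9.2.11.6 says: "Initiation and stopping of renal replacement therapy can occur based on the" clinician's or institution's own protocols and judgement. Attribution of adverse events to study drug (11.1.5) is also judged at the site. If treating staff knew the arm, these judgements could differ between arms for reasons other than drug effect, and the analysis could not detect or correct that.

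**Working it through.** The plan states no figure on this point, so the check is a comparison of passages plus a vial count.

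**1. Does vial use identify the arm?**
Inputs: dose 0.50 mg/kg and 10 mg drawn per vial (4.3.1); placebo uses no trial vials (Synopsis, 4.3.2). Body weights are assumed.
Formula: vials = dose ÷ 10 mg, rounded up, with dose = 0.50 × weight.

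| Weight (assumed) | Dose | Active vials, no priming | Active vials, 5 mL priming (assumed) | Placebo vials |
|---|---|---|---|---|
| 50 kg | 25 mg | 25/10 → 3 | 30/10 → 3 | 0 |
| 80 kg | 40 mg | 40/10 → 4 | 45/10 → 5 | 0 |
| 100 kg | 50 mg | 50/10 → 5 | 55/10 → 6 | 0 |
| 120 kg | 60 mg | 60/10 → 6 | 65/10 → 7 | 0 |

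The protocol adds a priming volume without stating its size; 5 mL is only an illustration. The two ranges, 3 to 7 and 0, do not overlap, so a count linked to a patient settles the arm.

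**2. Do the custody rules respect the blind?**

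| Item in 8.1.4 | Assigned to | Against 7.2 and 8.1.3 |
|---|---|---|
| Retain, store and destroy vials | The Investigator, no delegate named | Conflict as written |
| Accountability log | The Investigator or a designated individual | Conflict if the Investigator keeps it; none if the unblinded preparer does |
| Per-patient dispensing log | A designated individual | Unspecified |
| Disposal instructions | The study monitor | Unspecified |
| Vial inventory and disposition | Unblinded monitor | Consistent |

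The last row shows that the protocol already treats sight of the vials as unblinding on the monitoring side. The pharmacy freezer in 8.1.2 covers unreconstituted drug; the section does not say where used vials are kept.

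**3. Could past allocations predict the next one?**
SAP 2.2 uses blocks of 2 or 4 within each site and stratum. Always guessing the arm that is behind is right, on average over a completed block:
- Block of 2: (0.5 + 1)/2 = 0.750.
- Block of 4: positions 1 to 4 are right with probability 1/2, 2/3, 2/3 and 1, giving (0.500 + 0.667 + 0.667 + 1.000)/4 = 0.708.

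These rates need lists that fill their blocks. With 120 patients, up to 90 sites and four lists per site, the planned average is 120/90 = 1.33 patients per site and 1.33/4 = 0.33 per list if all sites open. Most lists would then hold no patient or one, and the first patient on a list is an even guess.

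**The case against.** The best defence is that Investigator in 8.1.4 is shorthand for the responsible site party. The same section has the Investigator undertake not to dispense the product elsewhere, although preparation belongs to the pharmacist. On that reading the unblinded preparer would hold the vials and both logs, and nothing would conflict. This is plausible, but the vial sentences name no delegate, so a site following them literally gives vials to a blinded person.

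Other parts of the defence stand, and they rule out readings that a reader might be tempted to adopt:

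- **That the Investigator must keep the dispensing record.** The per-patient log goes to a designated individual, and the accountability log may be delegated. Only vial custody is assigned without an alternative.
- **That a blinded monitor is authorised to check accountability.** Section 13.5 does not label its monitor. It says the blind is respected, in the context of medical-record review, and 8.1.4 twice gives vial work to an unblinded monitor.
- **That the EDC exposes vial counts.** Section 13.4 speaks of drug dispensed, not vial numbers, and provides role-based access. Section 8.2 measures compliance by volume delivered, which is matched between arms. Protocol 12.5.5 and SAP 2.2 keep the allocation variable out of the managed clinical data.
- **That one look at stored vials is enough.** The documents describe no patient-labelled vials. Linking vials to a patient needs the log, or a count around a dosing date.

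It is also fair that dialysis decisions need not be made by the person holding the vials, and that survival and the algorithmic eGFR component leave less room for judgement.

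**Conclusion.** The conflict is real but narrow. Section 8.1.4 requires a person who must be blinded to keep and destroy material that shows the arm, and permits that person to hold the log linking it to patients. Sections 7.2 and 8.1.3 do not allow this. The passages must be reconciled.

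For any patient whose vial use can be linked, the arm is revealed without error: at least 3 vials against none, assuming weights of 50 kg or more. How often that would happen cannot be derived from the documents; it depends on how sites delegate. The open points in 8.1.4 (per-patient log and disposal), 13.4 and 13.5 need clarifying, but they do not show a breach.

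A reader might also infer that allocation is predictable 71% to 75% of the time. The planned number of patients per list does not support that, so prediction of the next allocation is a minor matter. The main risk is unblinding of patients already treated.

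**What to change.** - **Section 8.1.4, custody.** Name the unblinded pharmacist or unblinded preparer as responsible for retaining, storing, reconciling and destroying vials and for both logs. Require that vials and records be kept where blinded staff have no access.
- **Section 8.1.4, disposal, and section 13.5, accountability.** State that disposal instructions and all drug accountability checks belong to the unblinded monitor.
- **Section 13.4 and source documents.** Keep vial numbers, vial counts and disposition records in a restricted pharmacy file, outside blinded source documents and EDC views, until database lock. Infused volume and infusion times can stay, because volume is matched between arms.

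The cost is a wording amendment to these sections and matching text in the site's drug-handling instructions. The unblinded preparer and unblinded monitor are already in the plan, so no new role is needed, and neither sample size nor analysis changes.

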8.1.5 Disallowed Medications

Study participants should not receive immunosuppressant agents or chemotherapy and should not be given high doses of steroids (defined as >40 mg or 0.50 mg/kg prednisone (or steroid with equivalent activity)/day for ≥ 2 weeks (see Appendix G – Section 18.7).

NOTE: Adrenal replacement therapy (corticosteroids) is permitted in patients with septic shock at the discretion of the Investigator balancing the potential benefits and risks in this situation. The optimal treatment regimen in this setting is not resolved. Investigators are referred to current Surviving Sepsis Campaign guidelines (www.survivingsepsis.org) as a reasonable source of guidance for steroid replacement therapy in septic shock patients.

Use of agents that can cause significant nephrotoxicity (e.g. non-steroidal anti-inflammatory drugs (NSAIDS), aminoglycosides, colistin, amphotericin B) should be avoided where possible. A list of potentially nephrotoxic medications is provided in the Study Procedure Manual.

